180 glucose and insulin sensitivity (HOMA-IR), at 3, 6 and 12 months between the vagus nerve
181 cryoablation group and the lifestyle intervention monotherapy group.
182

183 The primary safety endpoint of the trial is occurrence of death and all procedure related
184 complications, such as bleeding, infection, pneumothorax, hemothorax, pulmonary injury,
185 complications of sedation, pain requiring hospital admission or treatment, dysphagia,
186 gastroparesis, nausea and vomiting, and gastrointestinal ulceration for the duration of the study.
187

188 Secondary outcomes include differences between treatment groups in any of the following
189 measures:

- 190 1. Body mass index (BMI), waist circumference, and waist-to-hip ratio at 3 and 6 months
191 compared to baseline
- 192 2. Lipids (total cholesterol, LDL, triglycerides) at 6 months compared to baseline
- 193 3. Systolic and diastolic blood pressure at 3 and 6 months compared to baseline
- 194 4. Daily caloric intake as measured by 3-day food recall compared to baseline at 3 and 6
195 months.
- 196 5. Changes in antihyperglycemic medication regimen compared to baseline at 3 and 6
197 months.
- 198 6. Appetite, hunger and satiety scoring by visual analog scale at baseline, 1 week, 1 month,
199 3 months and 6 months
- 200 7. Physical activity questionnaire (IPAQ) at baseline, 3 and 6 months
- 201 8. Fasting glucose and insulin levels at 3 and 6 months compared to baseline

202 203 **C. STUDY DESIGN:**

204 This is a randomized, controlled, unblinded clinical study in obese adult patients with T2D,
205 HbA1c 7.5-10.5%, BMI 30-40 kg/m² treated with non-insulin antidiabetic medications with

207 stable doses for at least 3 months.

208 Subjects will be pre-screened with the relevant questions from the Three Factor Food
209 Questionnaire by phone or in person to determine eligibility prior to consent. Following consent
210 and screening for trial eligibility, subjects will be randomized to treatment group. The primary
211 endpoint, glycemic control, will be assessed at 6 months post-procedure. Patients will be
212 recruited from the diabetes clinic at Grady Memorial Hospital and Emory University Clinics.
213

[figure not shown]
214 We will be screen up to 40 participants to be able to randomized 30 patients, they will be
215 enrolled in this pilot exploratory study. Patients will be randomly allocated to undergo either CT

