216 guided cryoablation of the vagus nerve plus lifestyle intervention or lifestyle intervention alone.

217 **Group 1:** CT guided cryoablation of the vagus nerve plus lifestyle intervention (n=15).

218 **Group 2:** Lifestyle intervention by trained RD/CDE (n=15).

219 All subjects will have the procedure performed at Grady Memorial Hospital or Emory University
220 Hospital Midtown or Johns Creek by trained study personnel.
221

222 The study schema is shown below. Both groups will undergo screening for eligibility followed
223 by randomization. If the subject is not fasting at time of initial consent and screening, he/she will
224 be brought back for a subsequent visit with fasting blood work. Subjects must be randomized
225 within 4 weeks of the screening visit. If the randomization visit falls outside of the 4 week time
226 frame, the subject must undergo repeat screening procedures. In- person lifestyle counseling will
227 be provided at baseline visit for both groups. Those undergoing cryoablation will receive a phone
228 call 24 hour post-procedure to evaluate for any immediate complications, 1 week in person
229 follow up visit, as well as a safety call at 2 months. Subjects in both groups will have weekly
230 contact with RD and in person follow up visits at 4 weeks, 3 months, and 6 months. Blood work,
231 anthropometric data and questionnaires will be administered at baseline, 3 months, and 6 months.
232 Safety follow up appointments will be scheduled at 9 months and 12 months, though no further
233 lifestyle counseling will be provided after 6 months. Questioning regarding adverse events and
234 side effects will occur at all visits, as well as assessment of glycemic control. Anti-
235 hyperglycemic medications will be adjusted at visits under the direction of the endocrinologist,
236 or as needed for clinically significant hypo- or hyperglycemic events.

237
238

239 Blood work will be as follows: For all lab parameters, subject results must be within the
240 reference range unless otherwise specified by inclusion/exclusion criteria or if assessed by study
241 physician to be not clinically significant.

Lab test	Baseline	3 months	6 months	9 months	12 months
Complete metabolic panel	X	X	X	X	X
Pregnancy test	X	X	X	X	
HbA1c	X	X	X	X	X
Lipid panel	X		X		
Insulin level	X	X	X		X
TSH	X				

242
243

D. STUDY PROCEDURE:

244 **Cryoablation procedure (to be performed by [name] or [name]):** Subjects will

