245 be NPO for 12 hours prior to the ablation procedure. Metformin and sulfonylureas will be held
246 the evening prior to the procedure. Subjects will present to the Interventional Radiology pre-
247 procedure holding area at 8:00 AM on the morning of the procedure and will have a peripheral
248 IV placed by nursing staff. Point of care blood glucose level will be checked; the procedure will
249 be deferred for BG >250 mg/dl until diabetes control can be better optimized. Low doses of
250 sedation will be used with IV versed and fentanyl. An Interventional Radiology nurse will
251 monitor the subject while sedation is being administered. Skin will be numbed using lidocaine.
252 The procedure will be done under CT guidance and involves a 4-5 mm scalpel incision followed
253 by percutaneous probe placement about the posterior gastroesophageal junction (the location of
254 the posterior vagal trunk). The probe will create a zone of decreased temperature (-20 to -40°C)
255 involving the posterior vagal nerve fibers/plexus. The cryoablation process will include a 3-

256 minute freeze, followed by a 1-minute thaw, and a second 3-minute freeze and 1 minute thaw.
257 After the procedure, a sterile dressing will be applied, and subjects will be monitored for 12
258 hours.

259

260 **Lifestyle Intervention:** All subjects will receive standardized dietary and exercise counseling
261 from a registered dietitian and exercise physiologist ([name]). Participants will be counseled
262 to follow a low carbohydrate diet providing a moderate amount of carbohydrates per day (~100
263 g). Focus will be on increasing fruits and vegetables and decreasing refined sugars and processed
264 foods. Dietary counseling will include motivational interviewing, goal setting and nutrition
265 education.⁴⁴ Subjects will also be encouraged to slowly increase physical activity to at least 150
266 minutes weekly. The lifestyle intervention structure will include detailed counseling sessions at
267 baseline, 3 and 6 months. These sessions ideally will occur face-to-face, although telemedicine
268 visit (via zoom) will be permitted on case-by-case basis due to the COVID-19 pandemic. In
269 addition, there will be weekly phone calls or texts (participants' choice) providing a total of 26
270 points of contact recommended by the USPSTF (United States Preventive Services Task
271 Force).⁴⁵

272

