384 **Withdrawal Criteria:** The subject may withdraw at any time during the study by the primary
385 care provider or his/her own decision.

386
387 The subject may be withdrawn at the investigator's discretion due to a safety concern or for
388 contravention to the inclusion and/or exclusion criteria. Any subjects experiencing a Grade 3-5
389 AE as described will be withdrawn from the study. Reasons for study withdrawal will be tracked
390 and documented.

391
392 If a subject is withdrawn prior to completion of the 12 month study period, the subject will be
393 encouraged to keep follow up appointments with the study team for monitoring of adverse events
394 or until resolution of any adverse events related to the procedure.

395 **Data Safety Monitoring:** In addition, an independent data safety monitoring committee
396 (DSMC) will be established to serve as the primary data and safety monitoring group for the
397 trial. The DSMC will review unblinded interim safety data, evaluate whether the study should be
398 stopped or amended for safety or other reasons, and make such recommendations to the
399 investigators. In addition, the DSMC will provide input to the investigators concerning the study
400 protocol, statistical analysis plan, administrative conduct of the trial, and interpretation of the
401 final safety and efficacy data. The DSMC will meet every 6 months, and as needed in the event
402 of an unanticipated adverse device effect. At each meeting, the DSMC will review the incidence
403 of adverse events, severity of each, statistical considerations, and safety concerns (including
404 information on hypo- or hyper-glycemia)— as well as conduct of the trial and accrual goals.

405 **f. Potential benefits to the subject.** We believe that subjects receiving the interventional
406 treatment will benefit from modest weight loss and improvement in glycemic control. Subjects
407 who receive the lifestyle counseling are expected to achieve modest weight loss as well.
408 Furthermore, enrollment in clinical research studies and enhanced focus on glucose monitoring
409 has been shown to reduce complications associated with hyperglycemia.

410

411 **F. STUDY SUBJECT SELECTION:**

412 **Inclusion criteria:**

- 413 1. Males and females between the ages of 22-65
- 414 2. Diagnosis of T2DM for <10 years
- 415 3. HbA1c between $\geq 7.5\%$ and $\leq 10.5\%$
- 416 4. Treatment with non-insulin antidiabetic medications with stable doses for at least 3

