417 months, with failed prior attempts at dietary interventions to optimize diabetes control
- 418 5. BMI 30-40 kg/m²

419 6. Willing to comply with study requirements
420 7. Documented negative pregnancy test in women of child bearing potential and use of an
421 effective birth control method
422 8. Average score of ≥ 3 on questions 4, 8, 9, 13, and14 from the Three Factor Eating
423 Questionnaire, to be assess prior to consent via phone screen or in person.

Exclusion criteria:

1. Diagnosis of type 1 diabetes or history of diabetic ketoacidosis
2. Use of insulin therapy
3. Significant kidney disease (eGFR < 60 ml/min/1.73m²)
4. Current drug or alcohol addiction
5. Thyroid disease unless underlying diagnosis is primary hypothyroidism on stable medications for >3 months with TSH in reference range at time of screening visit
6. Systemic steroid use within 30 days prior to randomization
7. Use of prescription or over the counter weight loss medications within 6 months prior to randomization
8. Weight gain/loss >5% over the past 6 months
9. Previous GI surgery or abnormal GI anatomy which may limit technical feasibility of the procedure
10. Recent diagnosis of cardiovascular disease requiring PCI or CABG within the past 6 months
11. Abnormal pathologies or conditions of the GI tract, including peptic ulcers, hiatal hernia, active gallbladder disease, pancreatitis, cirrhosis, inflammatory bowel disease, upper GI bleed within 6 months of randomization
12. Any condition or major illness that places the subject at undue risk by participating in the study
13. Psychiatric condition rendering the subject unable to understand the possible consequences of the study
14. Inability to provide informed consent
15. Female subjects who have been pregnant within 6 months or breast-feeding at time of enrollment into the study, or women who plan to become pregnant within the next 12 months
16. Diagnosis of anemia, RBC transfusion in the preceding 3 months or expectation to receive transfusion within the next 12 months, or hemoglobinopathies that would affect HbA1c reliability
17. Active or recent infection
18. Immunosuppression
19. History of coagulopathy or high risk for development of deep vein thrombosis (including congestive heart failure, those who are non-ambulatory, active leukemia/lymphoma, prior thrombotic events, family history of thrombosis)
20. History of blood pressure instability (systolic BP \leq 100 or \geq 160 mmHg)

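### The withdrawal clause lets randomized subjects be removed for anatomy that only the cryoablation arm is imaged for, with no outcome follow-up planned for them

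*Combined protocol and SAP*

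**What the plan says.** Section III.C puts eligibility before allocation: after consent "and screening for trial eligibility, subjects will be randomized to treatment group". The screening it describes consists of questionnaire items and laboratory tests; a subject who is not fasting will "be brought back for a subsequent visit with fasting blood work". Neither the text nor the laboratory table lists CT, endoscopy or other imaging at this stage.

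Two exclusions in section III.F concern anatomy. Exclusion 9 reads "Previous GI surgery or abnormal GI anatomy which may limit technical feasibility of the procedure". Exclusion 11 begins "Abnormal pathologies or conditions of the GI tract, including peptic ulcers, hiatal hernia, active gallbladder disease".

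CT appears in section III.D as part of the cryoablation: "The procedure will be done under CT guidance and involves a 4-5 mm scalpel incision followed". Group 2 receives lifestyle intervention alone, and no imaging is described for it.

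Withdrawal Criteria, in section III.E, allows withdrawal at the investigator's discretion for a safety concern or for "contravention to the inclusion and/or exclusion criteria". The clause is not limited to the period before randomization. Reasons for withdrawal are to be recorded. Withdrawn subjects are encouraged to return so that adverse events can be followed; nothing is said about HbA1c or weight. The trial is unblinded (section III.D, Blinding).

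Section III.G compares 6-month HbA1c change between groups by a t-test or Wilcoxon test. It names no analysis set and no rule for withdrawn subjects.

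**The concern.** Chart and history can reveal known conditions in either arm before allocation. A condition nobody knew about has only one listed route to discovery, the CT at the procedure. That CT takes place after allocation and in one arm. A lifestyle subject with the same anatomy would not be discovered and would stay in.

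Read together, the provisions let entry criteria be applied a second time, in one arm, by staff who know the allocation. If withdrawn subjects then have no 6-month HbA1c, a t-test or Wilcoxon test on 6-month change omits them, and the arms compared are no longer the arms randomized. With 15 per group, one or two such removals are a visible share of an arm.

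**Working it through.** **The plan's own figure.** Section III.G allows 20% attrition: 15 × 0.8 = 12 per group, with 80% power at 1.2 SD. Alpha and sidedness are not stated; I assume two-sided 0.05. For a two-sample t-test the noncentrality is 1.2 / √(1/12 + 1/12) = 2.94 on 22 degrees of freedom, which gives power of 80.2%. The figure reproduces.

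**Chance of a one-sided finding.** The documents give no rate of undiagnosed disqualifying anatomy, so the prevalence p is an assumption, taken as 5%, 10% and 20%. The chance of at least one case among 15 is 1 − (1 − p)^15, and the expected number is 15p.

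**Bias.** If carriers differ from non-carriers by g SD in HbA1c change and all carriers leave one arm only, that arm's mean shifts by p × g. The documents give no g; I assume 0.5 to 1 SD.

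**Consistency with the pilot.** Section I reports 20 pilot subjects and complete technical success. If p applied there and a carrier counted as a technical failure, the chance of no case in 20 is (1 − p)^20.

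| p | Expected in 15 | At least one in 15 | Bias, g = 0.5 | Bias, g = 1 | No case in 20 |
|---|---|---|---|---|---|
| 5% | 0.75 | 54% | 0.025 SD | 0.05 SD | 36% |
| 10% | 1.5 | 79% | 0.05 SD | 0.10 SD | 12% |
| 20% | 3 | 96% | 0.10 SD | 0.20 SD | 1% |

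Section II gives ten pilot subjects instead of 20. With ten, the chance of no case at p = 20% is 0.8^10 = 11%. On either count 20% is the least compatible of the three values.

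In the worst corner, a 0.20 SD shift at 12 per arm raises the two-sided rejection rate under no effect from 5% to about 7.5%.

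**Power if such subjects are lost.** Removing 1, 2 or 3 further subjects from the cryoablation arm (11, 10 or 9 against 12) gives 78.3%, 76.0% or 73.3% at 1.2 SD.

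**Power if such subjects are kept.** Suppose k of 12 cryoablation subjects are untreated and gain nothing, with the SD unchanged. The mean difference becomes 1.2 × (12 − k)/12.

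- k = 1: 1.1 SD, power 73.1%
- k = 2: 1.0 SD, power 64.9%
- k = 3: 0.9 SD, power 55.9%

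**The case against.** The best reply is that nothing here is certain to happen. Withdrawal is discretionary, and the plan nowhere says that a withdrawn subject leaves the analysis. On that view the real gap is the missing analysis set, and CT findings only illustrate it. The first part stands, and it limits the claim to a permitted risk. The second stands only in part: the withdrawal clause is a written rule, it is open after randomization, and the follow-up attached to it serves safety only.

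It is also fair that the prevalence is assumed, that the pilot speaks against the high end, and that no passage links unfavourable anatomy to HbA1c or weight change. The pilot does not settle the rate, because its own screening is not described. The schema figure is not visible in the copy I worked from, so the absence of imaging before randomization is inferred from the text and the laboratory table. One sentence in section III.C speaks of all subjects having the procedure, but the group definitions beside it make clear that this concerns the site for Group 1.

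Several stronger readings are tempting and not supported:

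- A reader might infer that the cryoablation arm will end up as a selected group with favourable anatomy. The text permits this but does not require it.
- A reader might infer that the attrition allowance of 3 per arm (15 − 12) will be used up. That needs the 20% scenario, the least supported.
- A reader might infer that a feasibility result is inflated. Feasibility is a stated aim, and a heading in section III.E mentions a technical success rate, but no such endpoint is defined.
- A reader might think a pre-randomization chart check would solve it. Entry criteria already apply before allocation, and a chart cannot show an undiagnosed condition.

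**Conclusion.** The point holds as a risk that the plan permits. The sequence of screening without listed imaging, CT in one arm, an open-ended withdrawal clause applied by unblinded staff, and safety-only follow-up allows post-randomization removal in the cryoablation arm alone. The 6-month comparison would then omit those subjects unless their HbA1c is still obtained.

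On the assumed ranges, at least one case is more likely than not. The resulting bias is modest, at most about a sixth of the 1.2 SD design effect (0.20/1.2), and its direction cannot be derived from the documents. What is mainly at stake is the comparability of the arms, not the sample-size figure, which is sound on its stated terms.

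A reader might also infer that rescue insulin counts as contravening exclusion 2. Section III.E allows such rescue, and exclusion 2 can be read as an entry criterion only. The documents do not settle how the withdrawal clause applies, so these passages must be reconciled.

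**What to change.** In Withdrawal Criteria, separate not receiving or stopping the procedure from leaving the study. State that a randomized subject later found to contravene an entry criterion remains in follow-up, unless the subject withdraws from it, with HbA1c collected at 3, 6 and 12 months and weight at 3 and 6 months. Whether such a subject is treated is for the sponsor to settle.

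In section III.G, state that all such subjects are analysed in their assigned arm. Report by arm the number randomized but not treated, and include them in the denominator of any technical success rate that is reported.

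Separately, reconcile the rescue insulin provision in section III.E, exclusion 2 in section III.F and the contravention clause.

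The administrative cost is small: protocol wording, and measurements at visits already scheduled. The statistical cost is not trivial. As shown above, keeping 1, 2 or 3 untreated subjects with no assumed effect lowers power at 12 per arm from about 80% to 73%, 65% or 56%. The plan should disclose this as the price of comparing the arms as randomized. The wording should be settled before outcome data by arm are seen.

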329 will have a sterile bandage placed on the incision and will be monitored for 12 hours.

330 2. *Pneumothorax*: Estimated risk is <1%. We feel that the risk of pneumothorax is non-
331 significant given that this is a CT guided procedure, which will minimize any off target
332 risk. Should any complications arise, this will be visualized in real time on the CT scan
333 and immediate treatment will be provided.

334 3. *Sedation associated risks*: <0.5% risk. Conscious sedation using fentanyl and versed
335 will be used at standard procedural doses. Should any excess sedation occur, this will be
336 reversed immediately in the procedural suite.

337 4. *Off target ablation*: This refers to any inadvertent ablation of other nerves, estimated to
338 be <1.0% risk. This would be seen in real-time on CT guidance, and ablation could be
339 halted immediately to prevent complete nerve resection.

340 **Protection against risks:** Our strict inclusion and exclusion criteria for entry will help to
341 minimize risks. In addition, we will carefully monitor patients with a phone call 24 hours, and 2
342 months after the procedure, and a clinic visit at 1 week, 1 month, 3 months, 6 and 12 months.
343 Subjects will be monitored for specific procedure related complications or adverse events at each
344 visit. Subjects will also be provided with contact information for study personnel should any
345 events occur in between visits. Unscheduled events can be arranged to assess any urgent matters.
346 All AEs, regardless of whether or not they are related to the procedure and use of the device, will
347 be documented and reported to the IRB, DSMB, and FDA in a timeline as specified by the FDA
348 Code of Federal Regulations Title 21, section 812.150 reporting ([21CFR812.150\(b\)](#)). Outcomes
349 regarding hypo- and hyper- glycemia will also be collected and reported for safety monitoring.

350

351 Subjects with poorly controlled diabetes (A1c >10.5%) or a history of DKA will be excluded
352 from enrollment. Subjects will be educated on the potential for development of hypoglycemia.
353 Diabetic medications will be adjusted in event of hypoglycemia/hyperglycemia under the
354 direction of [name] (Endocrinologist). Self-monitoring of blood glucose (BG)
355 levels will be recommended twice daily and any time symptoms of hypo/hyperglycemia occur.
356 In the setting of hyperglycemia (average BG >250 mg/dl x 1 week), medication doses will be

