357 adjusted. Subjects on metformin will have the dose titrated to a maximum of 2000 mg/d if
358 tolerated. Sulfonylureas can be titrated to maximal doses per manufacturer instruction. Subjects
359 may be prescribed rescue therapy with insulin in the event of significant hyperglycemia
360 unresponsive to titration of oral agents. In the setting of BG <100 mg/dl, sulfonylurea doses will
361 be decreased by 50% and discontinued if necessary. If BG <55 mg/dl, sulfonylureas will be
362 stopped. Metformin will be stopped if hypoglycemia persists.

363

364 **Technical success rate of the procedure and procedure related complications:**
365 Discontinuation of the trial will occur if 3 participants within the first 8 of 30 planned experience
366 significant adverse events (AEs) (Grade 3 procedure-related AE or procedure-related serious
367 AE) at any point during follow-up and if 4 participants experience significant AEs (Grade 3
368 procedure-related serious AE) at any time. The trial will be stopped at any point if a Grade 4 or
369 Grade 5 AE occurs until determination can be made regarding its potential relationship to study
370 involvement.

371

372 **Grading of AEs:**

373

Grade 1	Mild; asymptomatic or mild symptoms; clinical or diagnostic observations only; intervention not indicated
Grade 2	Moderate; minimal, local or noninvasive intervention indicated; limiting age-appropriate instrumental ADL
Grade 3	Severe or medically significant but not immediately life-threatening; hospitalization or prolongation of hospitalization indicated; disabling; limiting self-care ADL
Grade 4	Life-threatening consequences; urgent intervention indicated
Grade 5	Death related to AE ⁶⁷

374

375 Specific clinical signs or symptoms that will qualify for the above criterial include (amongst
376 other potential Grade 3-5 AEs not listed here): constitutional symptoms (severe fatigue
377 interfering with ADLs, fever $> 40^{\circ}\text{C}$, prolonged and/or severe rigors), endocrine (uncontrolled
378 hyperglycemia, ketoacidosis), gastrointestinal (inadequate caloric intake requiring TPN or IV
379 fluids, diarrhea requiring IV fluids and/or manifesting as >7 stools/day, symptomatic abdominal
380 distention or bloating, severe abdominal pain requiring narcotics, ileus, severe nausea requiring
381 hospitalization, bowel obstruction or perforation), hemorrhage requiring intervention, infection
382 requiring antibiotics, or pain interfering with ADLs.

383

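### Mandatory study withdrawal after a Grade 3-5 adverse event, with no rule to keep HbA1c, can make missing 6- and 12-month HbA1c depend on glycemic outcome and on arm

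*Combined protocol and SAP*

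**What the plan says.** All references are to the combined protocol and SAP.

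- **Withdrawal (III.E, Withdrawal Criteria).** Any participant with a Grade 3-5 "AE as described will be withdrawn from the study". The preceding sentence leaves withdrawal for safety or eligibility reasons to the investigator's discretion; this one leaves none.
- **Qualifying events (III.E, Grading of AEs).** The endocrine entry reads uncontrolled "hyperglycemia, ketoacidosis), gastrointestinal (inadequate caloric intake requiring TPN or IV", with no glucose or HbA1c threshold. The list also covers ileus, perforation, severe abdominal pain, hemorrhage and infection.
- **After withdrawal (III.E, Withdrawal Criteria).** Participants are "encouraged to keep follow up appointments with the study team for monitoring of adverse events", or until procedure-related events resolve. HbA1c is not mentioned.
- **Handling of hyperglycemia on study (III.E, Protection against risks).** "In the setting of hyperglycemia (average BG >250 mg/dl x 1 week), medication doses will be" adjusted, and participants "may be prescribed rescue therapy with insulin in the event of significant hyperglycemia" that does not respond to oral titration.
- **Stopping rules (III.E).** The count-based rule concerns "significant adverse events (AEs) (Grade 3 procedure-related AE or procedure-related serious" events. For the higher grades, "The trial will be stopped at any point if a Grade 4 or" Grade 5 event occurs, until relatedness is decided.
- **Visits (III.C).** "Safety follow up appointments will be scheduled at 9 months and 12 months, though no further" lifestyle counseling follows month 6. HbA1c is tabled at baseline and at 3, 6, 9 and 12 months, and glycemic control is to be assessed at every visit. Nothing extends this to withdrawn participants. Only the cryoablation arm has the 24-hour call, the 1-week visit and the 2-month call.
- **Analysis (III.G).** HbA1c change at 6 months is compared by Wilcoxon or t-test, 6- and 12-month glycemic parameters by one-way ANOVA, and repeated-measures models are added. No analysis set, missing-data method or rule for values after withdrawal or rescue is given.

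**The concern.** Poor glycemic control is both the primary outcome and a named reason for leaving the study. A written rule, rather than chance dropout, could therefore decide whose 6- and 12-month HbA1c is missing. The 6-month test and the ANOVA use only observed values at the visit, so they would compare selected subsets of the arms.

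Two mechanisms pull in different directions:

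- **A hyperglycemia trigger common to both arms.** If cryoablation works, more controls cross it. The worst control outcomes drop out and the estimated benefit shrinks.
- **Procedure complications.** These arise only after cryoablation, and that arm has three additional safety contacts at which events can be found. This could remove more treated participants, with an effect on the estimate that depends on who they are.

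At stake is the effect estimate, which III.G says is meant to help plan larger trials, and safety follow-up. The procedure is given once, so withdrawal does not end exposure; it only loosens observation of the people who had severe events.

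**Working it through.** **1. The plan's own figure.** Inputs from III.G: 15 per group, 20% attrition, difference 1.2 SD. 15 × 0.80 = 12 per group. A two-sample t-test (two-sided 5%, an assumption because no level is stated) with noncentrality 1.2 / √(2/12) = 2.94 on 22 df has power 80.2%. The stated 80% reproduces. The attrition allowance covers lost numbers, not outcome-dependent loss.

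**2. Which grades matter.** Grade 5 is death, so no HbA1c can be kept. A Grade 4 or 5 event already halts the trial pending review. The avoidable loss is mainly Grade 3.

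**3. Bias from a common hyperglycemia trigger.** The documents give no event rate and no link between trigger and outcome, so everything here is assumed. Let Y be the 6-month change in SD units, N(0,1) in controls and N(−1.2,1) after cryoablation. A participant is lost if T = ρY + √(1−ρ²)·noise exceeds c, with c set so that 10% or 20% of controls are lost (c = 1.282 or 0.842). With λ(x) = φ(x)/Φ(x), the remaining difference is

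1.2 + ρ[λ(c + 1.2ρ) − λ(c)].

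Worked case, ρ = 0.5 and 10% lost: λ(1.282) = 0.195, λ(1.882) = 0.070, so 1.2 + 0.5 × (0.070 − 0.195) = 1.138.

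| ρ | Controls lost | Treated lost | Remaining difference (SD) | Bias (SD) |
|---|---|---|---|---|
| 0.2 | 10% / 20% | 6.4% / 14.0% | 1.188 / 1.182 | 0.01 / 0.02 |
| 0.5 | 10% / 20% | 3.0% / 7.5% | 1.138 / 1.101 | 0.06 / 0.10 |
| 1 (upper bound) | 10% / 20% | 0.7% / 2.1% | 1.023 / 0.901 | 0.18 / 0.30 |

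The standard error at 15 per arm is √(2/15) = 0.37 SD.

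**4. By count.** Removing the worst 1, 2 or 3 participants on T (simulation, 100,000 trials, difference 1.2 SD):

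| Starting size | Trigger | Power (1 / 2 / 3 lost) |
|---|---|---|
| 15 per arm, no other dropout | ρ = 0.5 | 86% / 85% / 83% |
| 15 per arm, no other dropout | random loss | 88% / 86% / 85% |
| 12 per arm, planned attrition already taken | ρ = 0.5 | 77% / 74% / 71% |
| 12 per arm, planned attrition already taken | random loss | 78% / 76% / 74% |

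Most of the power loss at ρ = 0.5 is therefore ordinary loss of numbers.

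**5. Type I error.** With no true effect and the pooled removals of step 4, rejection stays at 4.9-5.1%. Inflation needs a different pattern. Taking the worst 1 or 2 of 12 from one arm only gives 7.3% or 11.3%, and forcing the worst 1 or 2 out of each arm gives 7.2% or 8.8%.

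**6. What repeated measures recover.** A likelihood-based model with everyone's 3-month value (assumed 3-to-6-month correlation 0.5-0.7) moves the ρ = 0.5 results to 1.15-1.17 SD (10% lost) and 1.12-1.15 SD (20% lost), and the ρ = 1 results to 1.06-1.09 and 0.95-1.00 SD. Recovery is partial.

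**7. What keeping the values gives.** If rescue lowers HbA1c by R SD in those who trigger, the difference with all values kept is 1.2 − R × (control trigger share − treated trigger share). At ρ = 0.5 and R = 1 this is 1.2 − (0.100 − 0.030) = 1.130 and 1.2 − (0.200 − 0.075) = 1.075, against 1.138 and 1.101 if they are dropped. At R = 0.5, keeping gives 1.165 and 1.137, closer to 1.2 than dropping. At R = 1.5 it gives 1.095 and 1.012, further away. With a perfect trigger, keeping is closer to 1.2 at all three values of R.

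**The case against.** **The rule may cover only procedure-related events.** The grading table and symptom list stand under a heading about procedural success and complications, and they spell out the stopping criteria. *As described* may point back to that block; then hyperglycemia in a control triggers nothing. This reading is possible and lowers confidence. It is not conclusive: the count-based stopping rule states relatedness, the withdrawal sentence does not, and the Grade 4-5 halt covers any cause.

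**Rescue keeps people on study.** A reader might infer that every participant who becomes hyperglycemic is lost. The documents do not support that: titration and rescue insulin come first, and Grade 3 means severe. What stands is that no line separates rescued hyperglycemia from the uncontrolled kind, and in an unblinded trial staff who know the arm must draw it.

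**Follow-up is partly provided for.** Withdrawn participants are encouraged to attend, and glycemic control is assessed at visits, so some HbA1c may be obtained. Nothing requires it or says that it enters the comparison.

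**The link to 6-month HbA1c is assumed.** This stands. An early trigger that is then treated may say little about month 6, and at correlation 0.2 the bias is negligible.

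**The fix brings in rescue effects.** This also stands, as step 7 shows. Retention answers a treatment-policy question; it does not guarantee the no-rescue difference.

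**Conclusion.** The concern holds in a limited form. As written, the rule can make missing 6- and 12-month HbA1c depend on glycemic outcome and on arm, mainly through Grade 3 events. On the assumed rates, a common trigger with correlation 0.5 costs 0.06-0.10 SD, about a sixth to a quarter of one standard error (0.06/0.37 to 0.10/0.37); the range runs from negligible to 0.30 SD. The number of events is unknown and could be zero.

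Three stronger conclusions are tempting but unsupported:

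- **That the sample size is wrong.** The stated 80% power reproduces at 12 per arm.
- **That the bias has a known direction.** The shrinkage in step 3 models one item on the list. Procedure complications and the extra cryoablation contacts could tilt losses the other way, and the documents give no rates for weighing them.
- **That false positives are inflated.** With the pooled removals modeled, type I error stays near 5%. Imbalance between arms is plausible, but the inflated figures also need the lost participants to be the worst HbA1c outcomes in their arm, which the documents do not show.

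Severity: minor to should-fix. Confidence: medium, because of the possible procedure-related reading.

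**What to change.** Replace the mandatory withdrawal sentence in III.E with: *A Grade 3 or 4 AE is managed clinically and does not by itself end follow-up; surviving, consenting participants keep the scheduled HbA1c visits to 12 months.*

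If the oversight bodies want to keep the withdrawal rule, the minimum is one added sentence: withdrawn participants who consent have HbA1c measured at the 6- and 12-month appointments.

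In III.G, state that all these values are analyzed in the assigned arm, including those after rescue insulin (a treatment-policy comparison), and that rescue use is reported by arm.

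The benefit is a more complete as-randomized comparison and fuller safety follow-up after a one-time procedure. The change does not prevent voluntary withdrawal or loss to follow-up.

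The cost is re-review of the protocol wording, including a safety rule. HbA1c is already scheduled at these visits, so no visits or patients are added.
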